### 6.5.4. Concomitant Medications and Nondrug Treatments

Concomitant medications will be defined as medications that are utilized on or after first dose of study drug date. Medications with missing end dates are considered concomitant. Medications with missing start dates and non-missing end dates will be considered concomitant if the end date is on or after the first dose. Descriptive summaries will be reported.

## 6.6. Safety Summaries and Analyses

The safety data (eg, AEs, SAEs, physical examinations, laboratory tests) will be summarized in accordance with CDISC and Pfizer Standards (CaPS) using the Safety population as described in [Section 4](#). Descriptive summaries for continuous data will be provided. Safety data that will be specifically summarized include:

- Safety laboratory tests according to CaPS. Shift tables summarizing the changes in laboratory test results from baseline will be presented.
- Clinically significant changes in physical examination.
- AEs of Special Interest as identified in the Safety Narrative Plan.

### 6.6.1. Adverse Events

Adverse events will be summarized according to CaPS.

The number (%) of subjects who experienced TEAEs will be reviewed and summarized by relatedness to the study drug and severity grade. Descriptive statistics (number and frequency) will be provided for all adverse event summaries. No hypothesis testing will be carried out.

### 6.6.2. Laboratory Data

Descriptive statistics will be reported for observed and change from baseline laboratory measurements at each visit. Lab tests will be presented alphabetically within each of the following categories:

- Liver function tests;
- IGF-I, IGF-I SDS;
- Hemoglobin A1c.

For each of the following laboratory tests, a shift from baseline will be presented by visit:

- Safety labs (hematology with differential, blood chemistry, liver function tests);
- IGF-I, IGF-I SDS;
- Hemoglobin A1c;
- Urinalysis.

Categories will be 'Low', 'Normal', and 'High'.

For IGF-I, IGF-I SDS, box plots will be created by visit and treatment group.

The number and percentage of subjects with increases in any of the following will be summarized at each visit and anytime post-baseline:

- ALT >2xULN, >3xULN, <5xULN;
- AST >2xULN, >3xULN, <5xULN;
- Bilirubin >3xULN and ALT >2xULN;
- Bilirubin >3xULN and AST >2xULN.

Two eDISH (evaluation of Drug Induced Serious Hepatotoxicity) scatter plots will be produced: maximum bilirubin vs. maximum ALT and maximum bilirubin vs. maximum AST.

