8.4.2. Potential Cases of Drug-Induced Liver Injury

Humans exposed to a drug who show no sign of liver injury (as determined by elevations in transaminases) are termed “tolerators,” while those who show transient liver injury, but adapt are termed “adaptors.” In some subjects, transaminase elevations are a harbinger of a more serious potential outcome. These subjects fail to adapt and therefore are “susceptible” to progressive and serious liver injury, commonly referred to as drug-induced liver injury (DILI). Subjects who experience a transaminase elevation above 3 times the upper limit of normal (\times ULN) should be monitored more frequently to determine if they are an “adaptor” or are “susceptible.”

In the majority of DILI cases, elevations in aspartate aminotransferase (AST) and/or alanine aminotransferase (ALT) precede total bilirubin (TBili) elevations ($>2 \times$ ULN) by several days or weeks. The increase in TBili typically occurs while AST/ALT is/are still elevated above $3 \times$ ULN (ie, AST/ALT and TBili values will be elevated within the same lab sample). In rare instances, by the time TBili elevations are detected, AST/ALT values might have decreased. This occurrence is still regarded as a potential DILI. Therefore, abnormal elevations in either AST OR ALT in addition to TBili that meet the criteria outlined below are considered potential DILI (assessed per Hy’s law criteria) cases and should always be considered important medical events, even before all other possible causes of liver injury have been excluded.

The threshold of laboratory abnormalities for a potential DILI case depends on the subject's individual baseline values and underlying conditions. Subjects who present with the following laboratory abnormalities should be evaluated further as potential DILI (Hy's law) cases to definitively determine the etiology of the abnormal laboratory values:

- Subjects with AST/ALT and TBili baseline values within the normal range who subsequently present with AST **OR** ALT values $>3 \times \text{ULN}$ AND a TBili value $>2 \times \text{ULN}$ with no evidence of hemolysis and an alkaline phosphatase value $<2 \times \text{ULN}$ or not available.
- For subjects with baseline AST **OR** ALT **OR** TBili values above the ULN, the following threshold values are used in the definition mentioned above, as needed, depending on which values are above the ULN at baseline:

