 - Preexisting AST or ALT baseline values above the normal range: AST or ALT values >2 times the baseline values AND $>3 \times \text{ULN}$; or $>8 \times \text{ULN}$ (whichever is smaller).
 - Preexisting values of TBili above the normal range: TBili level increased from baseline value by an amount of at least $1 \times \text{ULN}$ **or** if the value reaches $>3 \times \text{ULN}$ (whichever is smaller).

Rises in AST/ALT and TBili separated by more than a few weeks should be assessed individually based on clinical judgment; any case where uncertainty remains as to whether it represents a potential Hy's law case should be reviewed with the sponsor.

The subject should return to the investigator site and be evaluated as soon as possible, preferably within 48 hours from awareness of the abnormal results. This evaluation should include laboratory tests, detailed history, and physical assessment.

In addition to repeating measurements of AST and ALT and TBili, laboratory tests should include albumin, creatine kinase (CK), direct and indirect bilirubin, gamma-glutamyl transferase (GGT), prothrombin time (PT)/international normalized ratio (INR), total bile acids, alkaline phosphatase and acetaminophen drug and/or protein adduct levels. Consideration should also be given to drawing a separate tube of clotted blood and an anticoagulated tube of blood for further testing, as needed, for further contemporaneous analyses at the time of the recognized initial abnormalities to determine etiology. A detailed history, including relevant information, such as review of ethanol, acetaminophen (either by itself or as a coformulated product in prescription or over-the-counter medications), recreational drug, supplement (herbal) use and consumption, family history, sexual history, travel history, history of contact with a jaundiced person, surgery, blood transfusion, history of liver or allergic disease, and potential occupational exposure to chemicals, should be collected. Further testing for acute hepatitis A, B, C, D, and E infection and liver imaging (eg, biliary tract) may be warranted.

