All cases demonstrated on repeat testing as meeting the laboratory criteria of AST/ALT and TBili elevation defined above should be considered potential DILI (Hy's law) cases if no other reason for the LFT abnormalities has yet been found. **Such potential DILI (Hy's law) cases are to be reported as SAEs, irrespective of availability of all the results of the investigations performed to determine etiology of the LFT abnormalities.**

A potential DILI (Hy's law) case becomes a confirmed case only after all results of reasonable investigations have been received and have excluded an alternative etiology.

8.4.3. Exposure to the Investigational Product During Pregnancy or Breastfeeding, and Occupational Exposure

Exposure to the investigational product under study during pregnancy or breastfeeding and occupational exposure are reportable to Pfizer Safety within 24 hours of investigator awareness.

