9.4. Safety Analysis

- Adverse events (Screening, Visits 1, 2, 3, 4, 5, 6, 7, and follow-up);
- Injection site reactions (Visits 1, 2, 3, 4, 5, 6, 7);
- Injection device complaints (Visits 1, 2, 3, 4, 5, 6, 7);
- Vital signs (Screening, Visits 1, 3, 4, 6, 7);
- Body weight (Screening, Visits 1 and 7);
- Physical exam (Screening, Visits 1, 3, 4, 6, 7);
- Urine pregnancy (if applicable) (Screening, Visits 1, 4, and 7);
- Routine clinical safety lab testing, IGF-I, IGF-I SDS, hemoglobin A1c, FT4 (Screening, Visits 4 and 7), somatrogon level (Screening, Visit 4² and Visit 7²), anti-somatrogon Ab (and neutralizing Ab) (Screening, Visit 4² and Visit 7²), and anti-rhGH Ab (and neutralizing Ab) (Screening, Visits 4 and 7).

Safety data will be tabulated and listed according to Pfizer's standard reporting algorithms.

² Only for subjects who have been on somatrogon for the previous 12 weeks of treatment.

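### The combined liver rows in SAP 6.6.2 match no threshold pair in Protocol 8.4.2, and the <5xULN entry for ALT and AST has no clear meaning

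*SAP*

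**What the plan says.** SAP 6.6.2 introduces a set of liver counts with this sentence: "The number and percentage of subjects with increases in any of the following will be summarized at each visit and anytime post-baseline". The list contains:

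- single-analyte entries, "ALT >2xULN, >3xULN, <5xULN", and the same three cut-offs for AST;
- two combined entries, "Bilirubin >3xULN and ALT >2xULN" and its AST counterpart.

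The section also plans two eDISH scatter plots: "maximum bilirubin vs. maximum ALT and maximum bilirubin vs. maximum AST". Its shift tables use only Low, Normal and High.

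Protocol 8.4.2 sets the laboratory thresholds for a potential DILI case:

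- **Normal baseline:** AST or ALT above 3xULN together with total bilirubin above 2xULN, with no evidence of hemolysis and alkaline phosphatase below 2xULN or not available.
- **Raised baseline AST or ALT:** "AST or ALT values >2 times the baseline values AND" above 3xULN, or above 8xULN, whichever is smaller.
- **Raised baseline bilirubin:** a rise of at least 1xULN from baseline, or a value above 3xULN, whichever is smaller.

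The SAP does not say that its rows implement Protocol 8.4.2, and it gives no reason for using a different pair.

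**The concern.** The SAP's combined rows carry the protocol's normal-baseline multipliers the other way round. That looks like a transposition, although the documents do not say so. These are the only bilirubin-plus-transaminase counts the SAP spells out, and no row in 6.6.2 uses bilirubin above 2xULN, alone or combined. A reader who sees zero in these rows could not conclude that nobody crossed the protocol's thresholds, and a non-zero count would not show that somebody had.

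The <5xULN entry is a second, separate problem. Placed in a list of increases, it may be a reversed sign, the top of a band above 3xULN, or a literal cut-off that also counts normal values. Two programmers could produce different tables from the same text. Under the band and literal readings, values of 5xULN or more have no row of their own.

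The frequency and severity of abnormal laboratory values is a named safety endpoint (SAP 6.2.4), so its liver counts should be readable against the protocol.

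**Working it through.** The plan gives no figure to reproduce; the check compares two logical rules. All values are multiples of ULN. The SAP's bilirubin is taken as total bilirubin, and the hemolysis and alkaline phosphatase conditions as met.

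**Rules.** Let t be ALT or AST, b bilirubin, a baseline transaminase and b0 baseline bilirubin.

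- SAP 6.6.2 combined rows: t > 2 and b > 3.
- Protocol 8.4.2, normal baseline: t > 3 and b > 2.
- Protocol transaminase threshold: 3 if a ≤ 1, otherwise min(max(2a, 3), 8).
- Protocol bilirubin criterion if b0 > 1: b − b0 ≥ 1, or b > 3.

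**Raised transaminase baseline.** a = 1.2 gives min(max(2.4, 3), 8) = 3. a = 2 gives 4. a = 4 gives 8. Over a from 0.1 to 15 the threshold runs from 3 to 8 and is never 2. The protocol's factor of 2 for transaminases multiplies the subject's baseline, not ULN.

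**Raised bilirubin baseline.** With ALT 4x and normal baseline ALT, the lowest qualifying bilirubin on a 0.1 grid is:

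| Baseline bilirubin | Lowest qualifying bilirubin | In SAP combined row? |
|---|---|---|
| 0.8 (normal) | 2.1 | no |
| 1.2 | 2.2 | no |
| 1.5 | 2.5 | no |
| 2.0 | 3.0 | no |
| 2.5 | 3.1 | yes |

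Bilirubin above 3xULN therefore occurs in the protocol only as one alternative for a raised bilirubin baseline, and never paired with transaminase above 2xULN.

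**Overlap at normal baseline.** Split t and b each into ≤2, >2 to 3, and >3, giving 9 cells. The protocol covers (t >3, b >2 to 3) and (t >3, b >3). The SAP covers (t >2 to 3, b >3) and (t >3, b >3). They share 1 of the 3 cells that either covers, so neither rule contains the other.

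| ALT | Bilirubin | Protocol thresholds | SAP combined row |
|---|---|---|---|
| 3.5 | 2.1 | met | not counted |
| 4 | 2.5 | met | not counted |
| 10 | 2.5 | met | not counted |
| 2.1 | 3.1 | not met | counted |
| 2.5 | 3.5 | not met | counted |
| 4 | 3.5 | met | counted |

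**Readings of <5xULN.**

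| Value | Literal (<5) | Band (>3 to <5) | Slip for >5 |
|---|---|---|---|
| 0.8 | yes | no | no |
| 4 | yes | yes | no |
| 6 | no | no | yes |

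**Scale.** Protocol 9.4 schedules "Routine clinical safety lab testing, IGF-I, IGF-I SDS, hemoglobin A1c, FT4 (Screening, Visits 4 and 7"), which leaves two post-baseline occasions. About 90 subjects × 2 = 180 scheduled samples at most. If all 90 are treated in both periods, one subject moves a row by 1/90 = 1.1 percentage points.

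**The case against.** The strongest reply is that the two sections do different jobs. Protocol 8.4.2 is a rule for detecting and reporting cases, conditional on baseline, hemolysis, alkaline phosphatase and repeat testing. SAP 6.6.2 is a descriptive count that does not cite it. Different cut-offs for different purposes are not in themselves a contradiction. That stands as far as it goes: this is an unexplained mismatch, not a broken cross-reference, and transposition is only the likely explanation.

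The second reply is that nothing is hidden, and this also stands. A subject inside the protocol thresholds still appears in the ALT or AST >2xULN and >3xULN rows, on the eDISH plots and in the listings (SAP 5). Case reporting is protected separately: "All cases demonstrated on repeat testing as meeting the laboratory criteria of AST/ALT and TBili elevation defined above should be considered potential DILI", if no other reason has been found, and such cases are reported as serious adverse events. Standard outputs under CaPS (SAP 6.6) and the Safety Narrative Plan are not in the documents and may add other summaries. The SAP also does not tie these particular rows to the abnormal-laboratory endpoint. All of this limits the consequence but does not make the rows interpretable.

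The third reply is that the cell comparison does not measure frequency. That is correct: the cells are not equally likely, and the comparison shows only that the rules differ in both directions.

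The last reply is that a row built on the normal-baseline pair would still not reproduce 8.4.2. With baseline ALT 2x the protocol needs more than 4x, so ALT 3.5x with bilirubin 2.5x would be counted although it falls short. With baseline bilirubin 1.2x, a value of 2.1x is short of 2.2x. This is true, but the error runs one way. Every protocol transaminase threshold is at least 3xULN. A rise of 1xULN from a baseline above 1xULN always exceeds 2xULN. Such a row over-counts slightly and misses no case that meets the laboratory thresholds.

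**Conclusion.** The concern holds, at minor severity. The combined rows match no protocol pair and err in both directions: they omit transaminase above 3xULN with bilirubin above 2 and up to 3xULN (at normal baseline), and they include transaminase above 2 and up to 3xULN with bilirubin above 3xULN. The <5xULN entry is ambiguous as written and unsound if taken literally.

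The effect is limited to a few descriptive counts. The number of subjects affected cannot be derived from the documents; with about 90 subjects and two scheduled post-baseline liver tests, few are likely.

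**What to change.** Reconcile SAP 6.6.2 with Protocol 8.4.2:

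1. Tabulate ALT or AST above 3xULN with bilirubin above 2xULN. Either replace the current combined rows or add this row beside them with a stated reason for keeping both.
2. Footnote that the row uses the normal-baseline thresholds, so subjects with raised baseline values may be over-counted, and that it does not apply the hemolysis and alkaline phosphatase conditions.
3. For ALT and AST, change <5xULN to >5xULN, or define it as a band above 3 and below 5xULN with a separate row for 5xULN and above.

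The cost is a text edit and reprogramming of a few rows in one descriptive table. No new data are needed.

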### **6.6.3. Vital Signs**

There will be no vital signs summaries.

### **6.6.4. Electrocardiograms**

Not applicable.

### **6.6.5. Physical Examination**

Complete physical examination will be collected at screening. If there is a significant departure in the physical examination, it will be collected as an adverse event after the first dose of the study drug. Therefore, there will be no physical examination summaries.

#### **6.6.6. Somatrogon Concentrations**

Somatrogon concentrations will be measured in serum samples collected before treatment and then at either Visit 4 (Week 12) or Visit 7 (Week 24) at the end of the treatment period that subjects received somatrogon. Descriptive statistics (number, mean, median, sd) will be used to summarize concentrations for those who tested positive for anti-hGH or anti-somatrogon antidrug antibodies (ADA) and for those who did not test positive for either.

#### **6.6.7. Immunogenicity**

For the immunogenicity data, the percentage of patients with blood samples positive for ADA and neutralizing antibodies (Nab) will be summarized for each treatment period. It is anticipated that patients should not test positive for ADA and Nab to somatrogon at baseline nor during the first period if they are randomized to treatment with rhGH. For patients who are positive for ADA, the magnitude (titer), time of onset, and duration of ADA response will also be described, if data permit. In addition, efforts will be made, as appropriate, to examine possible effect of the ADA on somatrogon concentrations and safety.

The number and percentage of subjects with the presence of each of the following antibodies will be summarized at each visit in which the test was performed:

- Detection of anti-recombinant human GH (r-hGH) antibodies:
  - Neutralizing,
  - Non-neutralizing.
- Detection of anti-somatrogon antibodies:
  - Neutralizing,
  - Non-neutralizing.

Descriptive statistics will be reported for anti-r-hGH and anti-somatrogon antibody titers at each visit.

### **7. INTERIM ANALYSES**

No formal interim analysis is planned for this study. However, as this is an open-label study, the sponsor may conduct unblinded reviews of the data during the course of the study for the purpose of safety assessment, facilitating dose-escalation decisions, facilitating PK/PD modeling, and/or to support clinical development.

## 9. APPENDICES

### Appendix 1. Data Derivation Details

#### Appendix 1.1. Definition and Use of Visit Windows in Reporting

The visit windows are defined for analysis and reporting purposes only.

Laboratory endpoints will be defined within visit windows determined by the actual day of observation relative to first dose of study drug (Day 1), ie, the actual day = date of assessment – date of first dose of study drug + 1.

The contiguous windows will be used to avoid discarding data. Week will be the time unit with a few exceptions noted in the visit window definitions below.

Visit Label	TARGET VISIT DAY	VISIT WINDOW IN DAYS	
		LOWER	UPPER
Screening	≤0	-99	-31
Baseline / V1 (W0)	1	-30	1
V2 (Week 1)*	8	2	25
V3 (Week 6)	42	26	64
V4 (Week 12)	84	65	90
V5 (Week 13)*	92	91	109
V6 (Week 18)	126	110	148
V7 (Week 24)	168	149	195

Notes:

\*Phone call visits only.

Week 24 is the analysis time point.

In general, window size is ½ the duration of the time between the previous study visit and the next study visit.

Target Visit Day = Current Visit in weeks × 7 + 1.

[Visit Window in Days Lower] = Current Target Visit Day – [(Current Target Visit Day – Previous Target Visit Day – 1) ÷ 2].

[Visit Window in Days Upper] = Current Target Visit Day + [(Next Target Visit Day – Current Target Visit Day – 1) ÷ 2].

CCI [REDACTED]

[REDACTED]

[REDACTED]	[REDACTED]	[REDACTED]	[REDACTED]	[REDACTED]
[REDACTED]	[REDACTED]	[REDACTED]	[REDACTED]	[REDACTED]
[REDACTED]	[REDACTED]	[REDACTED]	[REDACTED]	[REDACTED]
[REDACTED]	[REDACTED]	[REDACTED]	[REDACTED]	[REDACTED]
[REDACTED]	[REDACTED]	[REDACTED]	[REDACTED]	[REDACTED]
[REDACTED]	[REDACTED]	[REDACTED]	[REDACTED]	[REDACTED]
[REDACTED]	[REDACTED]	[REDACTED]	[REDACTED]	[REDACTED]
[REDACTED]	[REDACTED]	[REDACTED]	[REDACTED]	[REDACTED]
[REDACTED]	[REDACTED]	[REDACTED]	[REDACTED]	[REDACTED]
[REDACTED]	[REDACTED]	[REDACTED]	[REDACTED]	[REDACTED]

[REDACTED]

[REDACTED]

CCI [REDACTED]	[REDACTED]	[REDACTED]	[REDACTED]	[REDACTED]
[REDACTED]	[REDACTED]	[REDACTED]	[REDACTED]	[REDACTED]
	[REDACTED]	[REDACTED]	[REDACTED]	[REDACTED]

[REDACTED]

[REDACTED]	[REDACTED]	[REDACTED]	[REDACTED]	[REDACTED]
[REDACTED]	[REDACTED]	[REDACTED]	[REDACTED]	[REDACTED]
	[REDACTED]	[REDACTED]	[REDACTED]	[REDACTED]
	[REDACTED]	[REDACTED]	[REDACTED]	[REDACTED]

[REDACTED]

[REDACTED]

CCI [REDACTED]	[REDACTED]	[REDACTED]	[REDACTED]	[REDACTED]
			[REDACTED]	
	[REDACTED]	[REDACTED]	[REDACTED]	[REDACTED]
[REDACTED]	[REDACTED]	[REDACTED]	[REDACTED]	[REDACTED]

[REDACTED]

[REDACTED]

CCI [REDACTED]	[REDACTED]	[REDACTED]	[REDACTED]	[REDACTED]
[REDACTED]	[REDACTED]	[REDACTED]	[REDACTED]	[REDACTED]
[REDACTED]	[REDACTED]	[REDACTED]	[REDACTED]	[REDACTED]

[REDACTED]

[REDACTED]

**Appendix 2. Questionnaires Used in the Study**

The questionnaires DCOA 1, DCOA 2, PGIS-IDA, and their schedule on daily activities administration to each sub-group within this study are not included again within this SAP. Please refer to the Protocol for the actual instruments or their schedule as shown below:

Instrument	Source within Protocol
Dyad Clinical Outcome Assessment Questionnaires	Appendix 3
Patient Global Impression Severity-Impact on Daily Activities	Appendix 4
Schedule of Dyad Clinical Outcomes Assessments and Patient Global Impression Severity-Impact on Daily Activities Administration to Each Sub-group	Appendix 5

**Appendix 3. List of Abbreviations**

Abbreviation	Term
ADA	anti-drug antibodies
AE	adverse event
BLQ	below the limit of quantitation
BP	blood pressure
CaPS	CDISC and Pfizer Standards
CDISC	Clinical Data Interchange Standards Consortium
CTP	C-terminal peptide
DCOA	Dyad Clinical Outcome Assessment
EMA	European Medicines Agency
FAS	full analysis set
FDA	Food and Drug Administration (United States)
GHD	growth hormone deficiency
hCG	human chorionic gonadotropin
hGH	human growth hormone
HRQoL	health-related quality of life
IGF-I	insulin-like growth-factor-I
IGF-1 SDS	insulin-like growth-factor-I standard deviation score
IM	intramuscular
MedDRA	Medical Dictionary for Regulatory Activities
N/A	not applicable
NAb	neutralizing antibodies
PGIS-IDA	Patient Global Impression Severity-Impact on Daily Activities
PD	pharmacodynamic(s)
PK	pharmacokinetic(s)
PPS	per protocol set
PRO	patient-reported outcome
rhGH	recombinant human growth hormone
SAE	serious adverse event
SAP	statistical analysis plan
SC	subcutaneous
SD	standard deviation
ULN	upper limit of normal
